5.5 Registry Data Collection

5.51 Research personnel approved by HMH will extract and organize data from the electronic health record into the database.

5.52 Data will be entered into the REDCap approved database only. All protected health information (PHI) will be handled to maintain HIPAA compliance. The REDCap system will store PHI but this information will not be exported for any analysis unless specifically approved by the IRB. In the REDCap forms, all PHI will be parked as “identifiers” and only deidentified datasets will not be exported and shared with anyone but the study team.

5.53 Key prognostic diagnostic fields, demographics, treatments, and outcomes will be populated with data. Structured and unstructured data in the patients’ electronic records will be reviewed to complete the population of the registry. The database however is not

intended to be an all-inclusive representation of the medical chart. Daily laboratories of routine nature will not be collected.

- 5.54 Adverse events may be scored and recorded using the common toxicity criteria (CTC). However, it will be the treating sites responsibility to report to the authorities/manufacturers any serious adverse events in accordance with standards of care for the institution and in compliance with local/national regulations.
- 5.55 This initiative is meant to be an observational database. No additional testing or treatment will be required for enrollment of a patient. All clinical care, including diagnostic and therapeutic decisions, will be at the sole discretion of the patient's treatment team.

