5.6 Variables

Data points will be collected from the electronic medical record (or other HMH sources as available for patients with confirmed or suspected COVID-19. A partial listing is detailed below:

- 5.61 Key demographic variables include age, gender, race, zip code, past medical history documented co-morbidities, smoking history, etc.
- 5.62 Key diagnostic variables include date of diagnosis (COVID testing), blood count at time of hospitalization and/or entry to ICU care, chemistry panel, ferritin, ddimer, c-reactive protein, IL-6 levels, etc.
- 5.63 Key therapeutic variables include use of hydroxychloroquine, azithromycin, ventilator support, dialysis support, pressor support, etc.
- 5.64 Key outcome variables include will include need for hospitalization, duration of hospitalization, need for icu/ventilator support, duration of icu support, and death..

5.65 Key treatment center variables include hospital type (academic/ community), number of cases per hospital.

Data Analysis

5.71 COTA will provide basic descriptive analysis of the COVID-19 patients in a de-identified aggregated fashion. Survival and healthcare utilization analysis with time variables will utilize censoring and the Kaplan-Meier methodology. Multi-variable analysis for associations between demographic and/or treatment variables and key outcomes will be performed. Additional analysis will be performed per review of the data.

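### Section 5.71 lets treatment comparisons go ahead without a time origin, a rule for discharge and death, or a commitment to adjust for presenting severity, site and calendar period

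*Combined protocol and SAP*

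**What the plan says.** Section 4.14 lists exploring the efficacy and toxicity of treatments, including off-label use, among the primary objectives. Sections 3.1 and 4 say the database should give early signals of what works and inform treatment choice.

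The analysis plan is section 5.71. Besides basic description and further analysis driven by review of the data, it has two substantive sentences: "Survival and healthcare utilization analysis with time variables will utilize censoring and the Kaplan-Meier methodology" and "Multi-variable analysis for associations between demographic and/or treatment variables and key outcomes will be performed". It gives no time origin, no list of censoring events, no rule for live discharge and no covariate set.

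Three other places bear on it:

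- **Exposure (5.63):** "Key therapeutic variables include use of hydroxychloroquine, azithromycin", followed by organ-support items. No start date is named, but section 5.6 introduces its lists with "A partial listing is detailed below".
- **Allocation (5.55):** "All clinical care, including diagnostic and therapeutic decisions, will be at the sole discretion" of the treating team.
- **Available covariates:** "Key demographic variables include age, gender, race, zip code, past medical history documented co-morbidities" (5.61); date of diagnosis, and labs at hospitalization and/or ICU entry (5.62); hospital type and case volume (5.65); site of care, presenting labs, presenting vital signs and oxygen need (Synopsis, item 1a).

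**The concern.** When clinicians choose the treatment, treated and untreated patients differ in severity, in hospital and in the phase of the epidemic. Most of the fields needed to deal with this are collected, but no sentence says they will be used. The only variables named for the multi-variable analysis are demographic and treatment variables.

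Timing raises a second problem. A patient must stay alive and in hospital long enough to start a drug. If exposure is a yes/no flag and follow-up runs from admission, the days before the drug started are credited to it.

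The third problem is the censoring rule. Discharge is an outcome in its own right (4.15), and a discharged patient is no longer at risk of in-hospital death. Censoring discharge as non-informative estimates a quantity that is not the in-hospital death risk. Length of stay has the same difficulty with death.

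At stake is whether a drug with no effect could be reported from this registry as helpful or harmful by an analyst who had complied with the protocol.

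**Working it through.** The documents give no event rate, sample size or effect size, so there is no plan figure to reproduce. Every input below is assumed and describes inpatients only. The drug has no effect throughout.

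**1. Discharge or death censored.** Assume constant hazards: death 0.025/day, discharge 0.10/day, total 0.125/day, horizon 28 days.

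- Kaplan-Meier mortality, discharge censored: 1 − exp(−0.025 × 28) = 0.503.
- Cumulative incidence of in-hospital death: (0.025/0.125) × (1 − exp(−0.125 × 28)) = 0.2 × 0.970 = 0.194.
- Kaplan-Meier discharge, death censored: 1 − exp(−0.10 × 28) = 0.939.
- Cumulative incidence of discharge: 0.8 × 0.970 = 0.776.

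Over a range of rates (death 0.01–0.02/day, discharge 0.08–0.12/day, 30 days), Kaplan-Meier mortality is 25.9%–45.1% against a cumulative incidence of 7.5%–19.0%.

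**2. Exposure counted from before it started.** Simulation of 1,000,000 patients per scenario with the rates just given, 60% destined for treatment, exponential start times with mean 1, 2 or 4 days, and 30 days of follow-up (12 scenarios).

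- Ever/never death rate ratio from admission: 0.57–0.82.
- Rate ratio with exposure counted from drug start: 0.99–1.01.

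The result depends on the estimator and the hazard shape. A second set of 12 scenarios used 30–70% destined and mean start at 1–5 days, with the rates in step 1 as its base case. The odds ratio for in-hospital death, ever versus never treated, was:

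| Hazard shape | Odds ratio |
|---|---|
| Constant | 0.99–1.01 |
| Deaths early (0.05/day to day 5, then 0.015) | 0.64–0.90 |
| Few early discharges (0.03/day to day 3, then 0.13) | 0.71–0.91 |
| Deaths late (0.01/day to day 5, then 0.04) | 1.1–1.5 |

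**3. Severity left out.** Assume 40% severe, with mortality 35% in severe and 8% in non-severe patients; 70% of severe and 35% of non-severe are treated.

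- Treated: (0.4×0.70×0.35 + 0.6×0.35×0.08) / (0.28 + 0.21) = 0.1148/0.49 = 0.234.
- Untreated: (0.4×0.30×0.35 + 0.6×0.65×0.08) / (0.12 + 0.39) = 0.0732/0.51 = 0.144.
- Odds ratio 1.83. With treatment shares reversed it is 0.55. With 50% versus 40% treated it is 1.19, and reversed 0.84.

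**4. Period left out.** Assume two equal periods with mortality 25% then 15%, and use falling from 70% to 20%.

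- Treated: (0.70×0.25 + 0.20×0.15)/0.90 = 0.228.
- Untreated: (0.30×0.25 + 0.80×0.15)/1.10 = 0.177.
- Odds ratio 1.37. If use rises from 20% to 70%, it is 0.73.

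In steps 3 and 4 the null holds within strata by construction. The odds ratios are crude, so they show the case in which nothing correlated with severity or period is adjusted for.

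**The case against.** The strongest reply is that this is a database protocol. Section 5.1 calls it descriptive, 4.14 says explore, the Synopsis has analyses done on request, and section 5.7 (Quality Control) warns about observational inference. On that view, time zero and covariates belong in the plan for each analysis. This lowers the weight, but it does not remove the point. Section 5.71 says that treatment-outcome association analysis will be done, and nothing in the documents requires a later plan.

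Several stronger readings are tempting, and the documents do not support them:

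- **The plan calls for ever/never comparisons, or Kaplan-Meier curves by treatment.** Neither appears. Ever/never is an inference from an exposure worded as use, and 5.71 ties Kaplan-Meier to survival and utilization, not to treatment groups. Its provision for additional analysis leaves room for time-dependent or competing-risk methods.
- **Severity will be omitted.** Multi-variable implies some adjustment, and comorbidities count as demographics in 5.61. What is missing is the commitment.
- **Start dates are not collected.** The list is partial, and 5.1 says fields for treatment regimens exist.
- **Follow-up stops at discharge.** No text says so; survival is collected, partly prospectively.
- **Every listed severity field can serve as a baseline covariate.** Only labs and vital signs are described as presenting. Oxygen need has no time attached, and 5.62 allows labs from ICU entry. Adjusting for values that arise after drug start would introduce a new bias.
- **Admission can be time zero for everyone.** Eligibility (5.3) does not require hospitalization, and 5.64 makes hospitalization an outcome.

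It is also fair to say that the illustrations measure known biases and not this registry, and that one of them (in-hospital proportions under constant hazards) shows none.

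**Conclusion.** The concern holds as a gap in specification that should be fixed before treatment comparisons are reported. An analysis can comply with 5.71 and still be confounded by severity, site or period, misplace exposure time, or censor a competing event. The plan allows these choices without prescribing them.

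No size can be given for this registry. On the assumed inpatient inputs, the competing-event error is large (50% against 19%). The exposure-timing and confounding errors run in either direction, from odds ratios of about 0.55 to 1.83, and can be close to nil. Age and comorbidity adjustment would remove part of the crude confounding; how much cannot be computed from the documents. The competing-event result applies to in-hospital outcomes and assumes that death after discharge is not counted.

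**What to change.** 1. **Adjustment (5.71).** Commit treatment comparisons to adjust for age, comorbidities, presenting vital signs, presenting labs, site of care and calendar period of diagnosis. Use oxygen need and other labs only when measured before treatment start, not at ICU entry or later.
2. **Competing events (5.71).** For hospitalized patients, report in-hospital death, discharge, and ICU and hospital duration as cumulative incidence with discharge and death as competing events, in place of Kaplan-Meier with the competing event censored.
3. **Time zero and exposure (5.6 and 5.71).** Set time zero by population: admission for inpatients, diagnosis date for outpatients. Where drug start dates are available, use time-dependent or landmark exposure. Where they are not, report treatment-outcome results as descriptive associations only. Since analysis uses de-identified exports (6.1), day numbers from time zero and a period category can replace calendar dates if needed.

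**Cost.** Items 1 and 2 rest mostly on fields already listed and need protocol text and analysis work; the timing of oxygen and lab values has to be checked. Back-abstraction of start dates for all eligible patients (5.42) could be substantial, but it is optional under item 3, and Business Intelligence reports (5.1) may supply some dates. Intervals will be wider, and a landmark analysis drops patients who die or leave before the landmark. Confounding by severity at a later drug start will remain, because "Daily laboratories of routine nature will not be collected" (5.53).

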5.7 Quality Control

Unlike traditional data sources (ie, claims databases) the full medical record is analyzed by the abstractors allowing deep medical variables to be characterized. The principal investigators and COTA will perform statistical reviews to uncover “obvious” inaccuracies. However, the data will not undergo formal secondary reviews for accuracy. Investigators should understand the limitations of an observational database in drawing any conclusions.

6 Protection of Human Subjects

This document is a study protocol for an observational database study. This study is to be conducted according to United States and international standards of Good Clinical Practice (CFR Title 21 parts 11, 50, 54, 56, 312, International Conference on Harmonization and the Declaration of Helsinki), applicable government regulations and Institutional research policies and procedures.

6.1 Informed Consent

The Principal Investigator believes that the elements for a full waiver of consent under 45 C.F.R. §46.116 are met. Specifically, in order to waive consent the following requirements must be met:

- (1) The research involves no more than minimal risk to the subjects;
- (2) The waiver or alteration will not adversely affect the rights and welfare of the subjects;
- (3) The research could not practicably be carried out without the waiver or alteration; as COVID-19 populations have received treatment and have been discharged or deceased.

The study protocol represents an observational review of patients with confirmed or suspected COVID-19. No interventions are required for enrollment of patients into this database. There will be no direct contact any patient. Protected health information (PHI) will not be made available (pursuant to the HIPAA Privacy Rule as described below) and only aggregate data will be disclosed. The data collection will be conducted across HMH network drawing information from a variety of healthcare settings, with data drawn principally from the electronic health records utilized by the network. It would not be practical (item 3) by the Investigators to obtain consent across the network (which includes multiple hospitals and clinics across the state) as no contact will occur between the study team and the potential subjects. This is an observational study. The subjects will be receiving standard of care therapy at multiple sites, with their consent for the care per usual practice, and will not be made aware of the collection of the data nor will their treating physicians as to keep the therapy unbiased by participation in this study.

Furthermore, this study will involve only collection of data that has or will be obtained for care of the patient/subject. Thus the study may be considered “secondary research” under the revised common rule that became effective January 2020. Unlike the pre-2018 rule exemption for secondary use of information and biospecimens, the Final Rule has no requirement that the information and biospecimens must be pre-existing at the time that the investigator begins the research; prospective collection is permitted.

Although the information will involve collection of the data from PHI and the REDCap database will need to have identifiers in place to permit data entry, the analysis will only be performed on de-identified datasets which will be exported to the research teams (COTA or other investigators). The REDCap system is HIPAA compliant and requires study team access. Identified datasets will not be shared. Thus the identifiers are not available to the research analytic teams and will not be shared.

Lastly, although not funded a governmental agency, the data may be shared with governmental agencies (including the CDC) as part of public health concerns.

6.2 HIPAA Privacy Rule compliance

The diagnostic evaluations and clinical outcomes of all patients with COVID-19 in HMH centers participating in this registry will be drawn from the EPIC system which contains PHI. The collected data will be entered into the REDCap system which will contain PHI. Both systems are secure, meeting HIPAA compliance, and may only be accessed by authorized personnel.

All data analysis will be conducted on exported de-identified data, under the secondary use clause. NO PHI will be publically disclosed unless requested by governmental agencies.

6.3 IRB

The Hackensack University Medical Center Institutional Review Board will serve as the IRB of record for this study for the Hackensack Meridian Network.

7 Disseminating and Communicating Registry Results

7.1

HMH, the principal investigator, and/or HMH sub-investigators may choose to publish information in the medical literature and/or at national meetings based on this registry. Any investigator will be required to recognize the data source in compliance with the journal standard practice. NO PHI may disclosed. If PHI is to be shared with other HMH investigators regarding separate IRB retrospective projects, this will be identified and written in the separate IRB approved protocol.

7.2

HMH, the principal investigator, and/or HMH sub-investigators may release data (de-identified) or analytic findings to governmental agencies as requested.

7.3

The HMH Biorepository (BioR) will be granted access to the database and any pre data, supplements or queries provided to the RWD study as the BioR is collecting the same clinical information from patients who have either provided consent for this collection or for any other specimens that have been acquired as per the BioR's protocol. The BioR will follow the internal SOP of the database and will not release personal health identifiers (PHI) to researchers.

7.4

The University of Miami will be granted access to only de-identified portions of the database as they are externally validating a risk score HMH has developed. They also will be developing a separate risk score on predicting intubation in COVID-19 patients and we anticipate an ongoing collaboration of sharing data

8 Data Ownership

Data contributed to the HMH registry will become the property of HMH. It may be utilized for commercial purposes by HMH in de-identified HIPAA compliant fashion.

9 References

1. Z Wu, JM. McGoogan: Characteristics of and important lessons from the coronavirus disease 2019 (COVID-19) outbreak in China: summary of a report of 72 314 cases from the Chinese Center for Disease Control and Prevention. JAMA (2020 Feb 24), 10.1001/jama.2020.2648
